**Figure 1. Study schema and primary measurements to be conducted during the sulindac intervention study.** All participants will have an initial one-month washout period prior to a 3-month observation period during which they will discontinue NSAID use and be monitored for adherence to the trial and undergo baseline MR imaging at two time points. For the intervention period, participants will undergo MR imaging after initiating sulindac at 6 and 12 months. Participants will complete the participant reported outcome (PRO) questionnaires, return drug logs, undergo standard laboratory testing, and receive additional study drug at these visits. Blood and urine as well as clinical measures of blood pressure will be obtained at baselines, and at 3-, 6-, 9- and 12-month on sulindac to bank for analysis of metabolite levels and prostanoids. In those who consent, breast biopsies will be obtained at baseline 2 and after 6-month on sulindac for exploratory analyses of proliferation, apoptotic, cellular and whole genome expression changes in response to agent.

month observation no NSAID period, will be used to identify participant likely not to adhere to the study

regimen and to determine the extent of variability in BD over time. **The study schema for the sulindac intervention is shown in Figure 1.**

#### 4.2 Objective 2

In addition to the intervention arm, a total target population of 75 breast cancer patients, matched on characteristics to the sulindac intervention study, are being recruited to an observation arm (hereafter referred to as 'observation' group) for the primary purpose of determining change in BD while on AI for 12 months as determined by our novel MRI-based imaging approach to generate a non-radiative, non-contrast of a fat to water map of the breast using FWMRI.

In healthy postmenopausal women, the mean age-related change in BD by mammography at 2-yrs has been reported from randomized trials to be -1.3% ( $\pm 2.9\%$ ). Studies of women on AIs have shown that AI use for 12 months does not *significantly* decrease BD beyond that of the age-related change in the contralateral breast of breast cancer patients when compared to a placebo control (see Table 1).

Table 1. Effect of Aromatase Inhibitors on Breast Density in Randomized Studies

Study	Agent	Mean change in BD	P value	Summary
Vachon et al. 2007 (Vachon et al. 2007)	Letrozole	-2.7%	p=0.96	No statistically significant therapy-by-subgroup interactions (for BMI and age at entry)

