	Placebo	-3.0%		
Cigler et al. 2010 (Cigler et al. 2010)	Letrozole	-0.01% (95% CI -3.89, 3.87)	p=0.69	No statistically significant therapy-by-subgroup interactions (for BMI and age at entry)
	Placebo	-1.32% (95% CI -8.86, 6.22)		
Cigler et al. 2011 (Cigler et al. 2011)	Exemestane	-0.17 (95% CI -4.34, 4.00)	P=0.37	No statistically significant therapy-by-subgroup interactions (for BMI and age at entry)

-2.93  
Placebo (95% CI -8.70,  
2.85)

---

[figure not shown]
These data support our intent to assess change in BD with sulindac intervention using each woman as her own control taking into consideration a 3% decrease due simply to age (see Study Design Sulindac Intervention Study). To insure that this is indeed the case when using the FWMRI methodology, an observation group, matched on characteristics to women in the sulindac intervention group, has been added to specifically measure 12 months change in BD by FWMRI. Findings from the observation group will be considered in the interpretation of findings from the sulindac intervention arm *but the observation arm is not serving as a control for the sulindac intervention.* The expectation is that we will observe on average a 2-3% average decrease in BD by FWMRI at 12 months in the observation group.

After initiating the sulindac intervention under the assumption of no more than a 3% annual decrease in BD, we were approached by the NCI to conduct a separate study in a population similar to that of the sulindac group to specifically determine the magnitude of change in BD by FWMRI in women on AIs at 6 and 12 months considering time on AI. This is both to provide an estimate for interpreting our intervention study using the new methodology and to provide information on AI effect on BD at 6 months using a more sensitive method of measurement.

Thus, the observation-only arm is being recruited to determine the effects of AI alone as well as time on AIs on: 1) BD as measured by fat/water (FW) and diffusion-weighted (DW) magnetic resonance imaging (MRI) as a secondary, exploratory analysis. DWMRI is obtained at the same time as the FWMRI and does not add additional participant burden. The schema for the observation study is shown in Figure 2.

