NCT01761877

Unique Protocol ID: 1RO1 CA1615301A1

Secondary IDs: 12-0080-04, 676847

Study Title: NSAID Effects on Clinical and Imaging Breast Biomarkers

Document Title: Statistical Analysis Plan

Last Modification 11/4/2019

Statistical Analysis Plan

Study Title: Effect of Sulindac on Breast Density in postmenopausal women taking aromatase inhibitors for treatment of their breast cancer.

Study PIs: [name] and [name]

Original Study. Our study was originally designed as a randomized, placebo-controlled study of the effect of sulindac (SUL) 150 mg BID on breast density (BD) measured by magnetic resonance imaging (MRD) in postmenopausal women taking adjuvant aromatase inhibitors (AIs). We hypothesized that SUL would lead to a decrease in BD after 12 months and that the decrease would be greater than that observed in the placebo arm. Secondary endpoints included effects of SUL on AI associated arthralgia, quality of life and breast tissue biomarkers. The original accrual targets were 75 in each arm.

Study Modifications. Major cuts to the study budget prior to initiation resulted in a revised study design and modification of the primary objectives. As a result, the primary study goals were modified 1) to obtain evidence for SUL action on BD using MRD measures and 2) to assess the tolerability and safety of SUL in the target population. The placebo arm was dropped, and the study was reduced to a single arm feasibility study based on extensive published evidence for no effect of AI therapy alone for 12 months on BD. At that time, a 4-week washout of non-steroidal anti-inflammatory drugs (NSAIDs) [except low dose aspirin] followed by a pre-intervention observation period of 3 months was introduced to establish the stability of BD measures over time. All planned tissue biomarker studies were dropped. The primary study objectives were modified to assess if SUL at 150 mg BID for 12 months showed evidence for any effect on BD and was well tolerated with secondary emphasis on an effect on blood pressure or arthralgia symptoms. In addition, the study design would allow us to report on: 1) within-patient MRD change over 3 months in the absence of intervention, 2) impact of baseline BD on any change in BD with SUL intervention and 3) the fraction of participants that would undergo repeat needle biopsy procedures.

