In consultation with NCI, concern was raised that prior studies of AIs showing no effects of AIs on BD were based on mammography and not the more sensitive MRI method under investigation. As such, an observational (non-randomized) control group comprised of BC patients stable on an AI was included specifically to monitor for AI effect on BD using the MRD method.

Initially, the target sample size was reduced to 75 and 60 in the intervention and observation groups, respectively. A previously planned futility analysis of SUL effect on MRD after 40 participants completed 12 months of intervention was changed to the primary analysis on limited resources and slow accrual. Patients consented to banking tissue biopsies for future biomarker studies.

Modified Study Hypotheses: Because of the modification to the study design, the study hypotheses were modified as follows:

Primary

SUL 150 mg BID for 12 months will decrease MRD in postmenopausal women taking aromatase inhibitor therapy.

- a. As a sensitivity analysis of this primary hypothesis, per-study analysis described below will also be performed using only subjects who are adherent with study protocols (adherence is defined as having taken at least 80% of study agent).
- b. As a sensitivity analysis of this primary hypothesis, per-study analysis for primary hypothesis will also be performed using only those subjects with baseline BD $\geq 15\%$.

Secondary

SUL 150 mg BID for 12 months will be well tolerated and grade 3 adverse events will not exceed 10% and patients who drop out secondary to adverse events will not exceed 10%. *With low sample size of 40, only when there are no grade 3 AE or drop out secondary to AEs, can say it will not exceed 10% (point estimate is 0% with 95% Blyth-Casella-Still CI (0-7.78%).*

Reportable Outcomes

1. Change in BD from baseline at 6 and 12 months by MRD in postmenopausal women receiving AI for treatment of breast cancer and 95% confidence interval will be reported separately for:
 - a. participants in the sulindac group who started sulindac and who had at least one MRD measure on intervention,
 - b. participants enrolled and started in the observation arm with at least one MRD measure post baseline,
 - c. participants adherent to SUL intervention (same caveats as a), and

- d. in both arms but reported separately for participants with baseline BD $\geq 15\%$ (same respective caveats as a and b).

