the same subject will be selected with the Akaike Information Criterion. Log-transformed BD at each time point will be used as the outcome with adjustment for log-transformed baseline BD to improve efficiency and hence power for modeling % change in BD directly.

Note: *There is no prespecified plan to conduct a statistical test comparing change in BD between the two study groups.*

Only subjects who start SUL intervention will be included in the primary analysis. This allows us to evaluate the effect of SUL in those individuals who start intervention. 95% confidence intervals of BD change at month 6 and month 12 in the SUL group will be reported.

There are few patients whose MRD could not be obtained because of image artifact. As a sensitivity analysis, multiple imputation will be used to impute all missing MRD using patients' baseline information such as age, race, BMI, cancer stage, chemotherapy and radiation therapy information, AI use and NSAID use. Ten imputed datasets will be generated and all estimates about BD% change will be constructed using Rubin's rule. All analysis for primary hypothesis will be repeated among a subgroup of patients whose baseline BD $\geq 15\%$ and further using only SUL patients with $>80\%$ drug adherence.

For secondary hypothesis, all adverse events and severe adverse events from patients in the SUL group will be reported. The rate of patients with grade 3 or higher adverse events will be reported along with 95% Blyth-Casella-Still confidence interval.

For Reportable Outcomes

The linear mixed effect model fitted for the primary analysis will also be used to estimate the BD% changes and 95% confidence intervals at month 6 and month 12 within the observational group.

As part of this analysis for reporting purposes, we will describe the comparability of the intervention and non-random observation arm, continuous characteristics will be compared among study arms using Welch's two-sample t-test. Categorical variables will be compared using Chi-square test and exact p-values based on simulations may be reported if there is data sparsity. Any differences will be reported.

Percentage change in BD during the 3-month observation period in the SUL group will be reported with its 95% confidence interval (*i.e.* % change as $[BD \text{ at the end of observation period} - BD \text{ at the beginning of observation period}] / BD \text{ at the beginning of observation period}$).

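### The SAP's primary sulindac claim rests on the sulindac arm's own density change with no stated reference, although the Protocol expects density to fall without sulindac

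*SAP*

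**What the plan says.** **SAP.** Under Modified Study Hypotheses the primary hypothesis is "SUL 150 mg BID for 12 months will decrease MRD in postmenopausal women taking aromatase inhibitor therapy". Under Final Data Analysis Plan a linear mixed model is named as the means of testing it. The primary analysis is limited to women who start sulindac, and its output is that "95% confidence intervals of BD change at month 6 and month 12 in the SUL group will be reported". The same section states: "There is no prespecified plan to conduct a statistical test comparing change in BD between the two study groups". It names no null value, margin or rule for success. The SAP also reports the 3-month run-in change and the observation-arm change, each with a 95% interval. It lists a pooled model with a group-by-visit interaction.

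Under Study Modifications the single-arm design is justified by "extensive published evidence for no effect of AI therapy alone for 12 months on BD", and the SAP then describes how "an observational (non-randomized) control group comprised of BC patients stable on an AI was included specifically to monitor for AI effect on BD".

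**Protocol.** Section 4.2 says of healthy postmenopausal women that "the mean age-related change in BD by mammography at 2-yrs has been reported from randomized trials to be -1.3" per cent. It describes the intended design as "using each woman as her own control taking into consideration a 3% decrease due simply to age", and adds: "The expectation is that we will observe on average a 2-3% average decrease in BD by FWMRI at 12 months in the observation group". Sections 6.1 and 27.2 give an age-related decline of 1-3%. Section 7.3 frames the primary hypothesis as a larger decrease on sulindac than in the woman's own baseline period. The analysis text in section 27.1 tests this with a paired t test of slopes with and without sulindac.

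**The concern.** The hypothesis is causal, but the planned estimate is a before-after change in one arm. Such a change combines any drug effect with ageing, continued aromatase inhibitor (AI) therapy and drift in measurement. The Protocol recognised this and set the sulindac-free slope in the same women as the reference. The SAP removes that reference. A reader who sees an interval wholly below zero under a heading on hypothesis testing would take it as support for sulindac, even if the fall is no more than the Protocol expected without it.

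The SAP's justification for a single arm does not close the gap. The trials in Protocol Table 1 compared an AI with placebo and found no difference. That is not the same as no change over time.

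**Working it through.** **1. The Protocol's own power figures.** One-sample (paired) noncentral t, effect 0.368 SD:

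- n = 80, two-sided alpha 0.017: power 80.1% (stated 80%).
- n = 60, two-sided alpha 0.05: power 80.1% (stated as above 80%).

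Both reproduce. The second concerns a 3% fall in women who take no sulindac. So the Protocol's own calculation gives a within-arm analysis about four chances in five of showing a fall with no drug present.

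**2. Inputs for the check.**

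- n = 40: the SAP makes the analysis after 40 women complete 12 months the primary one.
- Background fall: 2-3 (Protocol 4.2). For comparison: 0.65 (the 2-year figure of 1.3, halved), and 0.01, 0.17 and 2.7 (the three AI arms in Table 1).
- SD of 12-month MRI change: not given. Section 27.2 equates 0.368 SD with a 3% fall in one place and 4% in another, implying 3/0.368 = 8.15 and 4/0.368 = 10.87. These rest on a cross-sectional conversion and are assumptions. A wider range adds 2.9 (the ± figure beside the 2-year change, read as an SD) and 15 (assumed).

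**3. Chance that the 95% interval lies wholly below zero with no drug effect.** With δ = (fall/SD) × √40 and critical value t(0.975, 39) = 2.023, the chance is P(T₃₉(δ) > 2.023). Example: fall 3, SD 8.15 gives δ = 0.368 × 6.325 = 2.33 and 62.2%. Results in per cent (nominal 2.5), falls in density points:

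| SD | 0.01 | 0.17 | 0.65 | 2 | 2.7 | 3 |
|---|---|---|---|---|---|---|
| 2.9 | 2.6 | 5.5 | 28.2 | 98.9 | >99 | >99 |
| 8.15 | 2.5 | 3.4 | 7.1 | 32.8 | 53.3 | 62.2 |
| 10.87 | 2.5 | 3.1 | 5.6 | 20.5 | 33.4 | 39.8 |
| 15 | 2.5 | 2.9 | 4.5 | 12.8 | 19.8 | 23.4 |

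The SAP models log density, and the Protocol does not say whether its 2-3% is in points or relative. Read as a relative fall, with an assumed SD of log change of 0.1-0.4, the chance is 5-47%.

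**4. What an explicit reference does.** If both groups truly fall by 3 points, the sulindac-minus-observation difference (40 v 60) is falsely positive in the drug's favour 2.5% of the time in simulation at either SD. Its SE relative to the single-arm change is √(1 + 40/60) = 1.29, or √(1 + 40/48) = 1.35 if 48 of 60 observation women complete. At 40 v 60, power for a 4-point difference is 66% (SD 8.15) or 43% (SD 10.87). It is not protected against confounding: a 1-3 point arm difference in non-drug decline (assumed) makes it falsely positive 9-43% or 6.5-27% of the time.

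**5. Precision of the Protocol's slope contrast.** With scans at 0, 3, 9 and 15 months, the annualised contrast is (m15 − m3) − 4(m3 − m0) = m15 − 5·m3 + 4·m0. For per-scan error SD s its error SD is √(1 + 25 + 16)·s = 6.48s, against √2·s for the on-sulindac slope alone. If the 1-2% between-measure variability in section 6.1 is s in points (assumed), then at n = 40 the SE is 1.02-2.05 and the 95% half-width about 2.1-4.1 points a year from measurement error alone.

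**The case against.** The strongest reply is that the SAP never says it tests against zero. It gives no null value or success rule for density, calls the trial a single-arm feasibility study, and says only that intervals will be reported. This stands to the extent that zero is an inference. It does not remove the point, because the SAP states a directional hypothesis, says the model is for testing it, and says the restriction to starters allows the effect of sulindac to be evaluated.

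Second, much of the safeguard exists. The run-in and observation-arm changes are reported with intervals, and Protocol 4.2, 6.1 and 27.2 say the observation change informs interpretation. That is true, but no SAP rule links either to the primary claim.

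Third, the background fall may be small. Two of the three AI arms in Table 1 changed by -0.01 and -0.17. The placebo arms fell by 3.0, 1.32 and 2.93, but the intervals given for the last two span zero (-8.86 to 6.22; -8.70 to 2.85). This also stands: the 2-3% fall is the Protocol's expectation, and Table 1 does not establish it.

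A reader might also infer that the lack of a between-group test breaches the Protocol. It does not: sections 4.2 and 27.2 say the observation arm is not a statistical comparator. Section 27.1, an earlier paragraph of 27.2 and the SAP's description of a control group read otherwise, so the documents need reconciling on its role.

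Finally, the SAP declares that its hypotheses were modified. The Protocol's January 2021 text concerns samples and laboratory relocation, so it does not show that the slope analysis was reaffirmed after the SAP of 11/4/2019.

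**Conclusion.** The point holds as a missing reference: the SAP drops the own-control contrast, states no alternative, and leaves a causal hypothesis to be judged by a before-after interval. The direction of the error is clear if density falls at all without sulindac. The size is not. With n = 40 and assumed SDs of 8.15 or 10.87, a 2-3 point background fall gives 20-62% against a nominal 2.5%; over SDs of 2.9-15 the range is 13% to nearly 100%; a background near zero gives little inflation.

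Two stronger readings are tempting. One is that the SAP would formally declare success on any interval below zero; it contains no such rule. The other is that 20-62% is the trial's false-positive rate; it depends on SDs and a background fall that the documents do not establish for 12-month MRI change. This should be fixed, with medium confidence about how much it matters in practice.

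**What to change.** 1. State in the SAP that the within-arm change is descriptive, that an interval excluding zero does not by itself support a sulindac effect, and that it is to be read against the observation-arm and run-in changes already reported.
2. Report the month-12 sulindac-minus-observation difference with a 95% interval from the group-by-visit term already in the pooled model, adjusted for baseline density, age, BMI and time on AI. Label it non-randomised and exploratory, and use it as context, not as a gate. Matching on age and AI duration was planned (Protocol 4.2), but eligibility and NSAID rules differ by arm (9.2, 15.1, 15.2).
3. Reconcile the SAP primary analysis with the slope analysis in Protocol 27.1. Reconcile the statements on the observation arm's role in Protocol 4.2, 27.1 and 27.2 and the SAP.
4. Label these changes post hoc if MRD results have already been reviewed. Protocol 4.4 says participation has concluded.

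Optional: report the Protocol's slope contrast as imprecise support. If the 8% interpretive bar in section 27.2 is carried into the SAP, define its scale, because it is set on Fra50 and not on density.

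The cost is wording and one contrast from a planned model, with no new data. The contrast is less precise (SE about 1.3 times that of the single-arm change at 40 v 60) and open to confounding, so it informs the reading but cannot decide it.
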